9.1.3. Protein Biomarkers

One 10 mL purple top (K₂EDTA) tube of blood will be collected on the days indicated within the Schedule of Assessments. Samples will be stored at approximately -70 °C and shipped to a third party laboratory for storage until the time of analysis. Duke University Medical Center will analyze plasma for several biomarkers including but not limited to VEGF, VEGF-R2, PIGF and sCD105 (Phase 1 Biomarker Laboratory, Duke University Medical Center, [name]). Please see the separate laboratory guide for further collection and shipment information.

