A hazard ratio (HR) of 0.67 is considered to be clinically relevant. Based on 1:1 randomization and the use of a one-sided log-rank test at the $\alpha=0.10$ level of significance, 115 events are required in order to have 80% power to detect a HR of 0.67. The expected PFS of patients treated with axitinib who have progressed following first line treatment with a VEGFR TKI is 4.8 months. Based on a planned accrual period of 12 months, and a minimum follow-up period of 4.3 months, approximately 150 patients will be required. Timing of the final analysis of PFS will be determined by the sponsor based on the expected total number of events that define PFS and the timing of these events, and may occur prior to the occurrence of 115 events.

5. Analysis Population

The safety population includes all patients who receive at least a portion of one dose of the study drug, TRC105 or axitinib (phase 2 portion).

The phase 2 study population for efficacy will include all randomized patients (intention to treat).

The Phase 1b study population for efficacy will include all patients who receive treatment with axitinib and TRC105.

6. General Analysis Comments

Summary statistics will include frequencies and percents of responses in each category for discrete measures; and may include means, medians, standard deviations, minimum and maximum values for continuous measures. Listings of data represented on the Case Report Form (CRF) will be provided.

SAS[®], Version 9.0 or higher or R version 2.15 or higher, will be used to perform all statistical analyses.

7. Missing Data

All data collected, including unscheduled visits, will be presented in the data listings. Summary tables will generally be limited to planned visits.

In all analyses, except for partial dates, it is expected that only observed values will be presented; no imputation of missing data will be conducted. Partial dates will be imputed according to the following table. CRFs that are not listed below are not expected to contain partial dates. CRF versions may change. Only if a change impacts the imputation of a partial date will the SAP be amended.

Planned Imputation Methods for Partial Dates

CRF	Field	Planned Imputation Method	
		Month and Year Given	Year Given
Adverse Events	Date of Onset	First of Month	Jan 01 of Year
	Date of Resolution	Last day of Month	Dec 31 of Year
Concomitant Medications	Start Date	First of Month	Jan 01 of Year
	Stop Date	Last day of Month	Dec 31 of Year

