Plasma levels of soluble angiogenic biomarkers will be listed by patient. Biomarker levels will be log-transformed before analysis, and analyses will be performed using baseline data from all available patients with continuous values for the protein analytes. PFS determined using univariate Cox proportional hazards models independent of treatment arm, and the resulting hazard ratios (HR), 95% confidence intervals (CI), and asymptotic P-values based on the score test will be reported. Multivariate Cox regression models will then test for interaction between marker level and treatment arm to identify markers predictive of benefit from axitinib or TRC105 and asymptotic P-values based on the Wald test for the interaction term will be reported. Biomarker levels will also be tested for interaction with each treatment arm separately. P-values will not be adjusted for multiple testing, and the results will be considered exploratory and hypothesis-generating. However, because high baseline levels of transforming growth factor-beta (TGF- β) receptor 3 and low baseline levels of osteopontin correlated with PFS and response rate in the Phase 1b study of TRC105 and axitinib, each of these biomarkers will be formally tested for correlation with PFS at the two-sided alpha level 0.05.

Hierarchical agglomerative clustering, using Euclidean distance and complete linkage, will be used to identify groupings among protein markers based on their baseline levels. The results will be illustrated using dendrograms. Forest plots will be created as illustrations of prognostic effect sizes (HRs and corresponding 95% CIs) with markers dichotomized as “high” or “low” relative to the median. Kaplan–Meier plots of PFS will also be created, with separate curves for each combination of treatment group by biomarker level. It has previously been shown in the Phase 1b study of axitinib and TRC105 that high baseline levels of TGF- β receptor 3 and low baseline levels of osteopontin correlated with PFS and response rate in the Phase 1b study of TRC105 and axitinib, so we will consider these biomarker levels dichotomized at the first quartile.

15. Changes from the Protocol-Specified Analysis

The details of analysis as indicated in this plan are based on the specifications of the 22Feb2016 version of the study protocol. Any later changes to the protocol may require consequential revision of this plan.

16. Programming Considerations

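### SAP section 14 clusters protein markers by Euclidean distance on log levels and specifies no centring or scaling, so the dendrogram depends on reporting unit and absolute abundance

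*SAP*

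**What the plan says.** SAP section 14 (Additional Analysis) sets out the baseline biomarker work. The preparation is: "Biomarker levels will be log-transformed before analysis". The clustering is then specified closely: "Hierarchical agglomerative clustering, using Euclidean distance and complete linkage, will be used to identify groupings among protein markers based on their baseline levels". The output follows: "The results will be illustrated using dendrograms". The objects being clustered are markers, not patients.

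Protocol section 9.1.3 describes the panel as "several biomarkers including but not limited to VEGF, VEGF-R2, PIGF and sCD105", with one named laboratory doing the assays. SAP section 14 adds TGF-beta receptor 3 and osteopontin. Neither document gives the number of markers, their units or their concentration ranges. Neither mentions centring, scaling, a common unit or a correlation-based distance. Protocol section 10.7 says only that the biomarker data will be listed.

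SAP section 14 also sets the status of the biomarker work, apart from two formal marker tests: "P-values will not be adjusted for multiple testing, and the results will be considered exploratory and hypothesis-generating".

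**The concern.** Different proteins can circulate at very different concentrations. Euclidean distance between two marker profiles mixes two things: how far apart their average levels are, and how differently they rise and fall across patients. If no centring is applied, the first can swamp the second. Two markers that track each other closely may be placed far apart because one is more abundant, or is reported in a different unit. Two unrelated markers at similar levels may be joined.

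What is at stake is the reading of the dendrogram. A reader will usually take a tree of angiogenic factors to show which ones behave alike. If level drives the tree, it shows assay scale and abundance instead.

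The other analyses in the section do not have this problem. Adding a constant to a log level leaves a Cox hazard ratio per log unit, a marker-by-treatment interaction coefficient, and a split at the median or first quartile unchanged. The log transform is enough for them, so nothing else in the section would alert a programmer that clustering needs a further step.

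**Working it through.** The plan gives no figure for the clustering, so there is none to reproduce.

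**Inputs from the documents.** Log transform, Euclidean distance, complete linkage, markers as objects (SAP section 14). About 150 patients, from SAP section 4.2 ("approximately 150 patients will be required"), used as the number of baseline samples.

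**Inputs assumed.** Log SDs, correlations, number of markers, and spread of mean levels. Natural logs are used. Another base multiplies every distance by the same constant and leaves the tree's shape unchanged.

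**Step 1: algebra.** For markers x and y with mean difference d in log level, SDs s_x and s_y, and correlation r, the squared distance per patient is

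d² + s_x² + s_y² − 2 r s_x s_y.

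Unit and abundance enter only through d, and correlation only through the last term. Moving one marker from ng/mL to pg/mL adds ln(1000) = 6.91 to each of its values, so d changes by 6.91 against every other marker. No assumption is needed for this.

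**Step 2: one pair against another.** With equal SDs the expression is d² + 2s²(1 − r). Take s = 0.6.

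- r = 0.9, tenfold difference in level: (ln 10)² + 2 × 0.36 × 0.1 = 5.30 + 0.07 = 5.37.
- r = 0, equal level: 2 × 0.36 = 0.72.

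The strongly correlated pair is the farther apart. The order reverses where d² + 0.2s² = 2s², that is, at a fold difference of exp(s√1.8). This is 2.0, 2.6 and 3.8 for s = 0.5, 0.7 and 1.0.

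**Step 3: whole tree.** Simulation with 150 patients, 12 markers in 3 correlation groups (r = 0.7 within a group, 0 between), log SDs between 0.5 and 1.0, and 300 replicates. Mean levels sit at three equally spaced points across the stated spread, with small jitter, and are assigned independently of group. Agreement is the adjusted Rand index (1 = identical grouping, 0 = chance).

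| Spread of mean levels (decades) | Log only: agreement with correlation groups | Log only: agreement with level groups | Share of squared distance due to mean level | Centred and scaled: agreement with correlation groups |
|---|---|---|---|---|
| 0 | 0.995 | 0.00 | 8% | 1.00 |
| 0.5 | 0.41 | 0.32 | 37% | 1.00 |
| 1 | 0.06 | 0.85 | 68% | 1.00 |
| 2 | 0.00 | 1.00 | 89% | 1.00 |
| 4 | 0.00 | 1.00 | 97% | 1.00 |

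Re-expressing a third of the markers in a unit 1000 times larger changes the log-only grouping (agreement between the two versions 0.21 to 0.26) and leaves the standardised grouping unchanged (1.00).

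**Step 4: sensitivity.** A second layout has 20 markers in 4 groups, r = 0.7 within a group, SD 0.6, and mean log levels varying between markers with a given SD. Log-only agreement is 1.00 at a level SD of 0 or 0.1, about 0.8 at 0.25, and 0.31, 0.07 and 0.02 at 0.5, 1 and 2. Doubling the marker SD to 1.2 softens the last three to about 0.8, 0.3 and 0.08. With weaker structure (r = 0.3 within, 0.15 between), agreement after standardising falls to about 0.8. The 1.00 in the table is therefore a feature of that setting and not a guarantee.

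**The case against.** Four points can fairly be made for the plan.

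First, the SAP is silent on standardisation and does not exclude it. A programmer might scale as a matter of routine. This stands: a reader might infer that the sponsor has chosen to cluster unscaled values, and the text does not show that. But the SAP fixes the transform, distance and linkage, and a run that follows those words exactly gives a unit-dependent tree.

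Second, the SAP says the groupings are based on baseline levels and nowhere says the aim is to find markers that vary together. This also stands, so it goes too far to say that the stated purpose is not met. It does not rescue the recipe, because a grouping by level would change with the reporting unit too.

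Third, the size of the effect is assumed. One laboratory runs the panel, and nothing shows that units are mixed or how far mean levels differ. If they are close, the log-only tree is nearly right. A reader might infer that any interpretation of the planned dendrogram would be wrong, and the documents do not support that.

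Fourth, little follows from it. The Cox models, interaction tests, forest plots, Kaplan-Meier plots and two formal marker tests all use single markers. The clusters feed none of them, and the Phase 2 figure list in SAP section 20.3 contains no dendrogram. This stands, and it sets the importance.

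**Conclusion.** The point holds as a limited one. SAP section 14 names no centring or scaling, and its recipe, run as written, yields a dendrogram that depends on reporting unit and absolute abundance. That part is algebra.

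The degree of distortion is conditional on assumed SDs, correlations and spread of mean levels. It is small when mean levels are nearly equal, mixed at about half a decade of spread, and level-driven from about one decade. The documents give no concentration ranges, so they do not settle where this panel falls. The tempting stronger conclusion, that the tree will group markers by concentration and not by co-variation, is not established.

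Importance is low. The analysis is exploratory, and no efficacy, safety or sizing conclusion depends on it.

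**What to change.** Add one sentence to SAP section 14: each log-transformed marker will be centred and scaled to unit SD across patients before Euclidean, complete-linkage clustering. Squared distance then equals 2n(1 − r), with the SD taken over n, so unit and abundance drop out. Complete linkage depends only on the ordering of distances, so markers merge in the same order as under a distance of one minus the Pearson correlation. The dendrogram heights differ between the two, so the SAP should say which is plotted.

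The cost is one line of code and no new data. There is a small downside: a marker with little real variation, or mostly assay noise, gets the same weight as an informative one. Centring alone would also remove the unit dependence, but distances would then still depend on each marker's SD. Naming the step in the SAP settles the choice before the data are seen.

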Appendix 1: Planned 105RC101 Tables

Appendix 2: Planned 105RC101 Listings

Separate tables and listings will be generated for the phase 1b and phase 2 portion of the study.

18. References

2. NCI Common Terminology Criteria for Adverse Events (CTCAE), Version 4.0.
http://www.acrin.org/Portals/0/Administration/Regulatory/CTCAE_4.02_2009-09-15_QuickReference_5x7.pdf
3. MedDRA: Medical Dictionary for Regulatory Activities terminology. Version 14.1. Reston, VA: Northrop Grumman, MedDRA MSSO.

19. Appendix 1 Tables

19.1. Tables in Text Phase 1b:

- Protocol Versions under which Each Patient was Treated
- Disposition of Patients by Treatment Group
- Incidence of Protocol Deviations by Treatment Group
- Demographics and Baseline Characteristics
- Screening ECOG Performance Status
- Past Cancer Treatment
- Primary Cancer Diagnoses by Dose Group
- Disease Present at Screening
- Best Overall Response and Duration of Response
- Summary of Serum TRC105 Pharmacokinetic Parameters Following Multiple Intravenous Infusions of TRC105
- Most Common ($n > 1$) and all Grade 3 and 4 Adverse Events by System Organ Class, by Preferred Term and by Grade and Dose Level
- Most Common ($N > 1$) and all Drug-Related Grade 3 and 4 Adverse Events by System Organ Class, by Preferred Term and by Graded Full Analysis Population and Dose Level
- Anti-Product Antibody (APA)

19.2. Appended Tables Phase 1b:

- 14.1. Demographic Data Summary Figures and Tables
 - 14.1.1. Patient Disposition
 - 14.1.3. Concomitant Medications
 - 14.1.4. Extent of Exposure to TRC105
 - 14.1.5. Extent of Exposure to Axitinib
- 14.2 Efficacy Data Summary Tables and Figures
- 14.3. Safety Data Summary Figures and Tables
 - 14.3.1. Displays of Adverse Events
 - 14.3.1.2. Number (%) of Patients with Treatment-Emergent Adverse Events
 - 14.3.1.3. Dose Limiting Toxicities
 - 14.3.1.4. Treatment-Emergent Adverse Events by Maximum CTCAE Grade
 - 14.3.1.5. Treatment-Emergent TRC105 Drug-Related Adverse Events by Maximum CTCAE Grade
 - 14.3.1.6. Treatment-Emergent Axitinib Drug-Related Adverse Events by Maximum CTCAE Grade
 - 14.3.1.7. Number (%) of Patients with Serious Treatment-Emergent Adverse Events
 - 14.3.1.8. Number (%) of Patients with Adverse Events Leading to Discontinuation
 - 14.3.2. Listings of Deaths, Other Serious and Significant Adverse Events
 - 14.3.3. Narratives of Deaths, Other Serious and Certain Other Significant Adverse Events
 - 14.3.3.1 Narratives of Deaths
 - 14.3.3.2 Narratives of Serious Unexpected Related Adverse Events
 - 14.3.4. Abnormal Laboratory Value Listing (Each Patient)
 - 14.3.4.1. Clinical Laboratory Results - Hematology: Change from Baseline
 - 14.3.4.2. Clinical Laboratory Results – Coagulation: Change from Baseline

14.3.4.3. Clinical Laboratory Results – Chemistry: Change from Baseline

14.3.4.4. Clinical Laboratory Results – Urinalysis: Change from Baseline

19.3. Tables in Text Phase 2 (by treatment group) :

- Protocol Versions under which Each Patient was Treated

Enrollment by country by Treatment Group

- Disposition of Patients by Treatment Group
- Incidence of Protocol Deviations by Treatment Group
- Demographics and Baseline Characteristics
- Screening ECOG Performance Status
- Past Cancer Treatment
- Primary Cancer Diagnoses by Treatment Group
- Disease Present at Screening
- Best Overall Response and Duration of Response
- Summary of Serum TRC105 Pharmacokinetic Parameters Following Multiple Intravenous Infusions of TRC105
- Most Common ($n > 1$) and all Grade 3 and 4 Adverse Events by System Organ Class, by Preferred Term and by Grade
- Most Common ($N > 1$) and all Drug-Related Grade 3 and 4 Adverse Events by System Organ Class, by Preferred Term and by Graded Full Analysis Population
- Anti-Product Antibody (APA)
- PFS by Central Review
- PFS by Investigator Assessment

Cox proportional hazard model of PFS

19.4. Appended Tables Phase 2 (by arm):

14.1. Demographic Data Summary Figures and Tables

14.1.1. Patient Disposition

14.1.3. Concomitant Medications

14.1.4. Extent of Exposure to TRC105

14.1.5. Extent of Exposure to Axitinib

14.3. Safety Data Summary Figures and Tables

14.3.1. Displays of Adverse Events

14.3.1.2. Number (%) of Patients with Treatment-Emergent Adverse Events

14.3.1.4. Treatment-Emergent Adverse Events by Maximum CTCAE Grade

14.3.1.7. Number (%) of Patients with Serious Treatment-Emergent Adverse Events

14.3.1.8. Number (%) of Patients with Adverse Events Leading to Discontinuation

14.3.3. Narratives of Deaths, Other Serious and Certain Other Significant Adverse Events

14.3.3.1 Narratives of Deaths

14.3.3.2 Narratives of Serious Unexpected Related Adverse Events

14.3.4. Abnormal Laboratory Value Listing (Each Patient)

20. Appendix 2 Listings

20.1. Appended Listings Phase 1b (by dose cohort):

16.1 Study Information

Listing 16.1.1 Listing of Informed Consent and Reconsent

Listing 16.1.3 Listing of IRBs and Sample Consent Forms

Listing 16.1.4 Listing of Investigators and Other Important Participants in the Study

Listing 16.1.5 Signature of Sponsor's Responsible Medical Officer

Listing 16.1.6 Listing of Patients receiving test drug from specific batches

Listing 16.1.9 Documentation of Statistical Methods

Listing 16.1.11 Publications Based on the Study

Listing 16.1.12 Important Publications Referenced in the Report

16.2 Patient Data Listings

Listing 16.2.1 Discontinued Patients

Listing 16.2.2 Table of Protocol Deviations

Listing 16.2.2.1 Inclusion Exclusion

Listing 16.2.3 Patients excluded from Efficacy Analysis

16.2.4 Demographic Data

Listing 16.2.4.1 Demographics

Listing 16.2.4.2 Disease Present at Screening

Listing 16.2.4.3 Primary Diagnosis

Listing 16.2.4.4 Prior Cancer Therapy

Listing 16.2.4.5 Time to tumor progression on most recent VEGF inhibitor therapy

Listing 16.2.4.6 Prior Cancer Surgery

Listing 16.2.4.7 Prior Cancer Radiation Therapy

Listing 16.2.4.8 Medical History and Baseline Emergent Adverse Events

Listing 16.2.4.9 Concomitant Medications

Listing 16.2.4.10 Concomitant Treatments

Listing 16.2.4.11 TRC105 Pre-Medications

16.2.5 Compliance and/or Drug Concentration Data

Listing 16.2.5.1 TRC105 Dosing Record

Listing 16.2.5.2 Axitinib Dosing Record

Listing 16.2.5.3 Final PK Report

16.2.6 Individual Efficacy Response Data

Listing 16.2.6.1 Overall Tumor Assessment

Listing 16.2.6.2 Duration of Stable Disease

Listing 16.2.6.3 Time to Progressive Disease or Death

Listing 16.2.6.4 Target Lesions

Listing 16.2.6.5 SPD (target lesions) over time compared to baseline

Listing 16.2.6.6 Non-Target Lesions

Listing 16.2.6.8 List of Scans

16.2.7 Adverse Event Listings (Each Patient)

Listing 16.2.7.1 All Adverse Events

Listing 16.2.7.2 Serious Adverse Events

Listing 16.2.7.3 Adverse Events Leading to Discontinuation

Listing 16.2.7.4 Adverse Events with an Outcome of Death

16.2.8 Individual Laboratory Measurements by Patient

- Listing 16.2.8.1 Abnormal Laboratory Results – Hematology
- Listing 16.2.8.2 Abnormal Laboratory Results – Coagulation
- Listing 16.2.8.3 Abnormal Laboratory Results – Chemistry
- Listing 16.2.8.4 Abnormal Laboratory Results – Urinalysis
- 16.2.8.5 Final Immunogenicity Report
- 16.2.9 Other
 - Listing 16.2.9.1 Vital Signs
 - Listing 16.2.9.2 Abnormal and Clinically Significant Physical Exam Results
 - Listing 16.2.9.3 ECG Results
 - Listing 16.2.9.4 ECOG Performance Status
 - Listing 16.2.9.5 Pregnancy at Screening
 - Listing 16.2.9.6 Archival Tumor Specimen
 - Listing 16.2.9.7 Drug allergies
 - Listing 16.2.9.8 Protein Biomarkers

20.2. Appended Listings Phase 2:

- 16.1 Study Information
 - Listing 16.1.1 Listing of Informed Consent and Reconsent
 - Listing 16.1.3 Listing of IRBs and Sample Consent Forms
 - Listing 16.1.4 Listing of Investigators and Other Important Participants in the Study
 - Listing 16.1.5 Signature of Sponsor’s Responsible Medical Officer
 - Listing 16.1.6 Listing of Patients receiving test drug from specific batches
 - Listing 16.1.9 Documentation of Statistical Methods
 - Listing 16.1.11 Publications Based on the Study
 - Listing 16.1.12 Important Publications Referenced in the Report
- 16.2 Patient Data Listings
 - Listing 16.2.1 Discontinued Patients
 - Listing 16.2.2 Table of Protocol Deviations
 - Listing 16.2.2.1 Inclusion Exclusion
 - Listing 16.2.3 Patients excluded from Efficacy Analysis
 - 16.2.4 Demographic Data
 - Listing 16.2.4.1 Demographics
 - Listing 16.2.4.2 Disease Present at Screening
 - Listing 16.2.4.3 Primary Diagnosis
 - Listing 16.2.4.4 Prior Cancer Therapy
 - Listing 16.2.4.5 Time to tumor progression on most recent VEGF inhibitor therapy
 - Listing 16.2.4.6 Prior Cancer Surgery
 - Listing 16.2.4.7 Prior Cancer Radiation Therapy
 - Listing 16.2.4.8 Medical History and Baseline Emergent Adverse Events
 - Listing 16.2.4.9 Concomitant Medications
 - Listing 16.2.4.10 Concomitant Treatments
 - Listing 16.2.4.11 TRC105 Pre-Medications
 - 16.2.5 Compliance and/or Drug Concentration Data
 - Listing 16.2.5.1 TRC105 Dosing Record
 - Listing 16.2.5.2 Axitinib Dosing Record
 - 16.2.5.3 Final PK Report
 - 16.2.6 Individual Efficacy Response Data

- Listing 16.2.6.1 Overall Tumor Assessment
- Listing 16.2.6.2 Duration of RECIST Response (PR/CR)
- Listing 16.2.6.3 Time to Tumor Progression or Death
- Listing 16.2.6.4 Target Lesions
- Listing 16.2.6.5 SPD (target lesions) over time compared to baseline
- Listing 16.2.6.6 Non-Target Lesions
- 16.2.7 Adverse Event Listings (Each Patient)
 - Listing 16.2.7.1 All Adverse Events
 - Listing 16.2.7.2 Serious Adverse Events
 - Listing 16.2.7.3 Adverse Events Leading to Discontinuation
 - Listing 16.2.7.4 Adverse Events with an Outcome of Death
 - Listing 16.2.7.5 Disposition (including Adverse Events) of Patients with a Serious or TRC105 related Adverse Event at Withdrawal
- 16.2.8 Individual Laboratory Measurements by Patient
 - Listing 16.2.8.1 Abnormal Laboratory Results – Hematology
 - Listing 16.2.8.2 Abnormal Laboratory Results – Coagulation
 - Listing 16.2.8.3 Abnormal Laboratory Results – Chemistry
 - Listing 16.2.8.4 Abnormal Laboratory Results – Urinalysis
 - 16.2.8.5 Final Immunogenicity Report
- 16.2.9 Other
 - Listing 16.2.9.1 Vital Signs
 - Listing 16.2.9.2 Abnormal and Clinically Significant Physical Exam Results
 - Listing 16.2.9.3 ECG Results
 - Listing 16.2.9.4 ECOG Performance Status
 - Listing 16.2.9.5 Pregnancy at Screening
 - Listing 16.2.9.6 Archival Tumor Specimen
 - Listing 16.2.9.7 Drug allergies
 - Listing 16.2.9.8 Protein Biomarkers

20.3. Figures Phase 2:

- 14.2.1 Kaplan Meier Survival Plot of PFS by arm
- 14.2.2 Kaplan Meier Survival Plot of PFS by arm where TGF β receptor III > median
- 14.2.3 Kaplan Meier Survival Plot of PFS by arm where TGF β receptor III < median
- 14.2.4 Kaplan Meier Survival Plot of PFS by arm where osteopontin > median
- 14.2.5 Kaplan Meier Survival Plot of PFS by arm where osteopontin < median
- 14.3.4.1 Clinical Laboratory Results – Hematology by arm over time (hemoglobin, white blood cell count, platelets)
- 14.3.4.2 Clinical Laboratory Results – Coagulation by arm over time (PT, INR)
- 14.3.4.3 Clinical Laboratory Results – Chemistry by arm over time (AST, ALT, Alk Phos, t bili, BUN, creatinine, calcium, phosphorus, glucose, lipase, TSH, amylase, sodium, potassium, chloride and bicarbonate)
